Safety Monitoring and Follow-Up	Subjects will be monitored and assessed for infusion related toxicity for the first 4hr. after the infusion and by telephone 24hr. after each infusion. Safety assessments will be conducted at the study follow-up clinic visits 6 and 12 months, and 2 years (telephone call) after the last HB-adMSC infusion, or more frequently if infusion related adverse events are suspected.
Statistical Analyses	The data will be analyzed using general linear mixed models (GLMMs) to estimate differences across time points (pre- and post-treatment).
Stopping Rules	
The stopping rules listed below will trigger cessation of enrollment and potential study closure pending a comprehensive DSMB safety review.
 
 1. Any infusion related death. 2. An infusion related, sustained (over 3 minutes) episode of hypoxia (SaO₂ of less than 80%) or the new requirement for mechanical ventilation. 3. Grade 4-5 CNS cerebrovascular ischemia event or Grade 4-5 seizure event as defined in the NCI CTCAE v4.0 occurring within 48 to 72 hours of the infusion. 4. Any Grade 4-5 Adverse Event as defined in the NCI CTCAE v4.0 and determined to be temporally related to the HB-adMSC infusion by the Medical Safety Monitor and/or DSMB.

ABBREVIATIONS

adMSCs-Adipose Derived Mesenchymal Stem Cells
ADL-Activities of Daily Living
AE-Adverse Event
ANAM-Automated Neuropsychological Assessment Metrics
ARDS-Adult Respiratory Distress Syndrome
CAT-Calibrated Automated Thrombogram
CBC-Complete Blood Count
CCI-Controlled Cortical Impact
CD142-Tissue Factor or Platelet Tissue Factor
CFU-Colony Forming Unit
CGMP-Current Good Manufacturing Practices
CFR-Code of Federal Register
CMP-Complete Metabolic Panel
CNS-Central Nervous System
CRF-Case Report Form
CRO-Contract Research Organization
CRU-Clinical Research Unit
CSF-Cerebral Spinal Fluid
CTCAE-Common Terminology Criteria for Adverse Events
CXR-Chest X-Ray
DSMB-Data Safety Monitoring Board
DTI-Diffusion Tensor Imaging
DVT-Deep Vein Thrombosis
EMR-Electronic Medical Record
ESC-Embryonic Stem Cells
ETOH-Ethanol/Alcohol
F-Fibroblast
FA-Fractional Anisotropy
FDA-Food and Drug Administration
GCP-Good Clinical Practice
GCS-Glasgow Coma Scale
GLMM-Generalized Linear Mixed Model
GM-Gray Matter
GOAT-Galveston Orientation and Amnesia Test
GOS-E-Glasgow Outcome Scale - Extended
HB-adMSC's-Hope Biosciences' Autologous Adipose-Derived Mesenchymal Stem Cells
HIPAA-Health Insurance Protection and Portability Act

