3.4 Visit #1: Screening & Consent

During this visit, and after consent has been obtained, the subject will undergo the following procedures:

1. Medical history including current medications and vaccinations,
2. Physical and neurological exam,
3. Vital signs (Heart Rate, BP, Respirations, Temp., SpO₂),
4. Blood samples for baseline clinical labs (CBC with diff., CMP, coagulation panel, renal function panel, urine hCG if applicable), and neuroinflammatory biomarkers and TSPO genotype,
5. Chest x-ray (AP, single view).
6. Baseline neurocognitive assessments.

The screening visit is anticipated to take about 4hr. to complete. The site PI/Co-PI will make the final determination on the subjects' eligibility and complete the inclusion/exclusion CRF. Ineligible

subjects will be notified by telephone and referred to their PCP for follow-up care if indicated. Subjects meeting study eligibility will be contacted by telephone to schedule the baseline imaging visit. The baseline imaging visit will be completed within 10 days of the screening visit.

Subjects entering the study from HSC-MS-16-0283 or HSC-MS-15-0744 will already be consented and will not have a blood sample drawn for their TSPO genotype.

Subjects will also be referred to a physician with Hope Biosciences who will perform the adipose tissue extraction. The adipose tissue extraction and processing will be performed under Hope Biosciences IND #18388 CMC procedures. Hope Biosciences' SOP for the adipose tissue extraction is provided in Appendix 1. If for any reason Hope Biosciences is unable to prepare the HB-AdMSC infusion (insufficient stem cells, contamination, etc.) the subject will be contacted and given the option to repeat the adipose tissue extraction or withdrawal from participation.

A staggered infusion visit plan for the 1st four subjects is included in Appendix 3

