4. PET/DT-MRI

Subjects and their care providers will receive instructions on administering SQ Lovenox (40mg once a day) for 7 days beginning the day before each infusion visit. Subjects will be asked to record the Lovenox injections on a log and return the form at the next study visit. A reminder call will be made to subjects the day before beginning each round of Lovenox. SQ Lovenox will not be required for subjects already taking an anticoagulant.

Subjects recruited from HSC-MS-16-0283 or HSC-MS-15-0744 will not be required to repeat the brain PET/DT-MRI for baseline imaging data.

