3.10 Participant Satisfaction Survey

Subjects or their care provider will be invited to complete an anonymous satisfaction survey in REDCap. The survey results will be used for the development of future clinical research studies requiring community based participatory research (CBPR) activities with the goal of improving research recruitment and retention.

Table 1a: Study Procedures

Study Procedures	Visit 1 Screening & Consent	Visit 2 Baseline Imaging	5 to 7 weeks for HB-AdMSC Processing	Visit 3 Inf. #1	Visit 4 Inf. #2	Visit 5 Inf. #3	Visit 6 6 Mo. Post-Inf. (+/- 21 Days)	Visit 7 1 Yr. Post-Inf. (+/- 21 Days)
Visit Location	CRU	HMRI		CRU	CRU	CRU	CRU / HMRI	CRU
Review of Medical History	X						X	X
Consent	X	X		X	X	X	X	X
Physical and Neuro Exam ¹	X	X		X	X	X	X	X
Vital Signs ²	X	X		X	X	X	X	X
Clinical Lab Evaluations ³	X			X	X	X	X	X
Research Blood Sample for TSPO Genotype	X							
Research Blood Sample for Neuroinflammatory Biomarkers	X						X	X
Neurocognitive/Functional Outcome Tests	X						X	X
Adipose Tissue Extraction ⁴ (Hope Bio. Clinical Facility)		X						
Prophylactic Lovenox ⁵				X	X	X		
Pre-Infusion Medications ⁶				X	X	X		
HB-AdMSC Infusion with 4hr. Observation ⁷				X	X	X		
Safety/Toxicity Assessments ⁸		X		X	X	X	X	X
Chest X-Ray (AP, Single View) ⁹	X							X
PET / DT-MRI Imaging ¹⁰		X					X	

1. Detailed Neuro exam optional on infusion visits based on physical exam and interval changes. **2.** Vital Signs: at baseline after consent, before and after the stem cell infusion, then q. 15min x 4, (1st hour), q. 30min. x 4 (next 2hrs.) then hourly until discharge, at follow-up visits, or more frequently if indicated.

3. CBC with diff, metabolic (CMP), coagulation and renal function panels, hCG (if applicable). **4.** Performed under Hope Biosciences IND #18388

procedures. **5.** Seven day course of prophylactic SQ Lovenox (40mg QD) beginning the day before each infusion visit. Subjects will receive a reminder telephone call the day before beginning each round of Lovenox. Lovenox will not be required for subjects already taking an anticoagulant. **6.** Benadryl

/Solumedrol (25mg for subjects <100kg or 50mg for subjects \geq 100kg.) I.V. 30 min. before infusion. **7.** Infusion given over a 1hr period (+/- 5 min.) with 14-day interval between study infusions (+/- 3 days). **8.** Assessment by telephone call 24hr. after each cell infusion and 24mo. after the last cell infusion. **9.**

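### The listed stopping rules are tied to the cell infusion, so a death or Grade 4-5 event from the required adipose extraction meets none of them, except possibly if it requires ventilation

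*Protocol*

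**What the plan says.** The stopping rules appear in the protocol synopsis. Their lead-in is a commitment: "The stopping rules listed below will trigger cessation of enrollment and potential study closure pending a comprehensive DSMB safety review". Four triggers follow.

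- Rule 1: "Any infusion related death".
- Rule 2: sustained hypoxia that is infusion related, or newly needed mechanical ventilation.
- Rule 3: a Grade 4-5 cerebrovascular ischemia or seizure event, in a window of 48 to 72 hours counted from the infusion.
- Rule 4: any Grade 4-5 adverse event "determined to be temporally related to the HB-adMSC infusion by the Medical Safety Monitor and/or DSMB".

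The trial also requires a tissue harvest. Section 3.3 counts the adipose extraction among the study procedures explained at consent, and the product is autologous, so no subject can be treated without it. Section 3.4 refers subjects to a sponsor physician for it and states: "The adipose tissue extraction and processing will be performed under Hope Biosciences IND #18388 CMC procedures". The sponsor's "SOP for the adipose tissue extraction is provided in Appendix 1". If the product cannot be prepared, "the subject will be contacted and given the option to repeat the adipose tissue extraction", or may withdraw. Tables 1a and 1b place the extraction before a column headed "5 to 7 weeks for HB-AdMSC Processing", which itself precedes infusion 1.

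Section 7.3 says that review by the Medical Safety Monitor (MSM), DSMB, IRB or sponsor may lead to suspension of enrollment after an adverse event.

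**The concern.** A stopping rule does more than serve the primary objective. It protects the next subject from a harm just seen in an earlier one. Here the next subject will undergo the same extraction, but the automatic halts are worded around the infusion.

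The gap is not about who judges the event. Rule 1 needs a death to be attributed and rule 4 needs an MSM or DSMB determination, so a judgement comes first in either case. The difference lies in what follows. Once an event is judged related to the infusion, enrollment must stop. Once it is judged related to the extraction, enrollment may stop. On the listed rules, further subjects could be enrolled and sent for extraction after a fatal or life-threatening extraction event, unless a reviewing body chose to suspend.

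**Working it through.** The stopping rules carry no event-rate threshold, alpha or power, so there is no plan figure to reproduce. The check sets each trigger against the timing and status of the extraction.

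**Timing.** From Tables 1a and 1b, the processing period is 5 × 7 = 35 days to 7 × 7 = 49 days. The longest time window in any rule is 72 hours, or 72 / 24 = 3 days. In the normal sequence the extraction therefore precedes infusion 1 by at least 35 days, far outside that window.

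**Rule by rule**, for a death or Grade 4-5 event caused by the extraction and occurring before infusion 1:

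| Rule | What it requires | Met? |
|---|---|---|
| 1 | Death related to the infusion | No |
| 2, hypoxia limb | Infusion-related hypoxia | No |
| 2, ventilation limb | Newly needed ventilation | No on the natural reading, where the opening qualifier governs both limbs; yes if the limb stands alone and ventilation was needed |
| 3 | CNS event within 48 to 72 hours of the infusion | No |
| 4 | Grade 4-5 event temporally related to the infusion | No; no infusion has yet been given |

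A repeat extraction would not normally change this, because it too supplies product for a later infusion. If one fell close to an infusion, rule 3 or 4 could catch an event by timing alone.

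**Other text available.** Section 4 (Risks) does not discuss the extraction. Section 6 names the MSM, the CRO monitors and the DSMB but adds no trigger in the paragraph available. Table 1a marks a safety assessment in the same visit column as the extraction. Table 1b, for subjects from the two feeder studies, puts the extraction at Visit 1 and shows its first safety mark at infusion 1. Recording an event would not in any case trigger a halt. Section 7.3 supplies the discretionary route.

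**Exposure.** From Section 8.1, 24 subjects × 1 extraction = up to 24 first extractions, plus any repeats. If the event occurred in the first subject, up to 24 − 1 = 23 others could still be due the same procedure. The documents give no complication rate, so the count measures exposure, not risk.

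**The case against.** The strongest objection is that much of the relevant text is not available. Section 6 is titled as the safety monitoring and reporting plan, yet only an overview paragraph can be read. Sections 2, 9 and 10 and the appendices cannot be read at all. The extraction has its own governance, through the sponsor's IND procedures and the Appendix 1 SOP, and a halt rule could well sit there. This stands, and it limits the finding to the four listed rules.

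A second objection is that the primary objective is infusional toxicity, so infusion-based halts are a coherent Phase 1/2a choice. That explains the wording. It does not protect the next subject referred for extraction.

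A third is that independent oversight would act anyway: Section 7.3 is not restricted to infusion events, and even a listed rule brings only a pause and possible closure. That lowers the practical stakes. But the same could be said of an infusion death, and there the sponsor chose to commit in advance.

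A reader might go further and infer that the protocol has no mandatory halt for extraction events anywhere. The documents do not support that, because the places where one would sit are not available. A reader might also infer that the rules should cover Lovenox, since each course runs "for 7 days beginning the day before each infusion visit" and so begins before infusion 1. That does not follow either: only 1 of 3 × 7 = 21 planned doses per subject precedes infusion 1, and rule 4 could be read to cover a bleed if the infusion goes ahead.

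**Conclusion.** The concern holds for the listed rules. An extraction-related death or Grade 4-5 event would meet no listed mandatory halt, with one possible exception: an event that required ventilation, if that limb of rule 2 is read on its own. It would be too strong to say that no listed rule could ever apply. In the text available, suspension after such an event is a matter of discretion.

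Up to 24 first extractions are exposed to the gap, plus any repeats; no probability of harm is claimed. The conclusion assumes the normal sequence, with extraction at least 35 days before infusion 1, and that the unavailable text holds no extraction trigger that already binds the trial. It is a low-priority point, a cheap improvement worth considering, and does not call the trial's safety oversight as a whole into question.

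**What to change.** Reword rule 1 to cover *any death related to the infusion or to the study-required adipose extraction*. Extend rule 4 to any Grade 4-5 adverse event that the MSM and/or DSMB judges related to the infusion or to the extraction. If a trigger for extraction events already exists in Section 6, an appendix or the IND #18388 procedures, cross-reference it in the stopping rules instead. The sponsor and DSMB would settle the final criteria.

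The cost is a wording change to two rules, using the existing MSM and DSMB, with no new visit, procedure or committee. The downside is an occasional extra enrollment pause for DSMB review.

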1. STUDY OBJECTIVES

The global objective of this study is to establish the safety and investigate the potential treatment effect of an intravenous infusion of HB-adMSC on brain structure, neurocognitive/functional outcomes, and neuro inflammation after traumatic brain injury and/or hypoxic-ischemic encephalopathy in adults.

1.1 Primary Objectives: Determine the safety of HB-adMSC as determined by infusional toxicity of the cell product.

Allogeneic MSCs have been used in numerous oncologic and non-oncologic clinical trials. They have an excellent safety profile that has been described in numerous publications. A recent meta-analysis evaluated 1012 patients with a variety of clinical conditions, and found only transient fever as an adverse event. (Lalu, 2012) However, other publications have raised an issue of a complement mediated induction of coagulation using human cells in vitro. (Moll, 2014) We and others have confirmed these findings, and have noted a Tissue Factor mediated pro-coagulant response associated with various types of MSCs with a wide variability related to CD142 expression. (Mangum, 2017; Christy, 2017, George, 2018) We propose evaluating the potential infusional toxicity of HB-adMSC in patients with sub-acute and chronic neurological injury.

1.2 Secondary Objectives: Obtain treatment effect estimates of HB-adMSC infusion on global gray and/or white matter as well as structural integrity of GM and WM regions of interest in the corpus callosum and corticospinal tracts as measured by fractional anisotropy (FA) and mean diffusivity (MD) in specific regions known to correlate with specific neurocognitive deficits in patients after neurological injury.

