4. RISKS

4.1 Respiratory Risks:

A concern exists regarding the intravenous infusion of large, adherent cells in a concentrated manner into a patient with a dysregulated systemic inflammatory response syndrome. A potential risk is amplification instead of diminution of the post-trauma pro-inflammatory response that typically manifest as exacerbation of respiratory failure or ARDS. Alternatively, the infusion could initiate a VTE event with subsequent cardiopulmonary sequelae of respiratory failure and/or right heart strain/failure. Infused cells will be evaluated for CD142 expression (cell number and intensity) and evaluated via in vitro thromboelastography for pro-coagulant activity. We plan to monitor oxygen saturation, and respiratory rate/work of breathing for the first 4 hours post-infusion. Chest x-rays will be obtained at baseline and the final study visit or more frequently if clinically indicated. We will re-examine the patient for VTE events (clinical exam, oxygen saturation) at each follow-up visit.

4.2 Hepatic Risks:

The reticuloendothelial system can sequester immature blood elements, theoretically resulting in hepatic injury. An acute elevation of the AST/ALT hepatic enzymes $> 900 \text{ U/dl}$ post-infusion will be considered an infusion related adverse event. This level is based upon the organ system scoring definitions for moderate hepatic failure and corresponds to the CTCAE v4.03 Grade 4 adverse event. It is unlikely that "end vessel" microthrombosis would occur in the liver due to the dual blood supply of the liver and the lung is the first pass organ. A comprehensive metabolic panel including AST/ALT will be drawn at each follow-up visit.

4.3 Neurologic Complications:

The patient's acute neurologic status will be evaluated at each study visit. A grade 4-5 CNS cerebrovascular ischemia event or Grade 4-5 seizure event as defined in the CTCAE v4.03 occurring within 4 hours of HB-adMSC infusion will be considered an infusion related adverse event. Other changes temporally related to HB-adMSC infusion (those events occurring within 48 to 72 hours of infusion) will be considered associated with the protocol and recorded as an adverse event.

4.4 Coagulation Cascade:

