7.3 Withdrawal of Subject from the Study Following Adverse Events

The PI will determine if an adverse event (AE) is of sufficient severity to require stopping subject participation. The subject (or LAR) may also voluntarily withdrawal from the study due to what he/she perceives as an intolerable AE. If the withdrawal from the study is due to an AE, the subject will be offered appropriate care under medical supervision until the symptoms of the AE resolve or the subject's condition becomes stable. Subsequent review by the MSM, DSMB, IRB or the study sponsor may also result in the suspension of further enrollment.

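### In the supplied text, no stopping rule names VTE or counts events, so repeated clots below Grade 4 would fire no pre-set rule and any pause would rest on discretionary review

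*Protocol*

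**What the plan says.** The stopping rules stand in the Protocol synopsis. Their preamble says that they "will trigger cessation of enrollment and potential study closure pending a comprehensive DSMB safety review". The four rules are:

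1. any infusion-related death;
2. an infusion-related fall in oxygen saturation below 80% for more than 3 minutes, "or the new requirement for mechanical ventilation";
3. in the 48 to 72 hours after an infusion, a Grade 4-5 cerebrovascular ischemia or seizure event;
4. more broadly, "Any Grade 4-5 Adverse Event as defined in the NCI CTCAE v4.0 and determined to be temporally related to the HB-adMSC infusion", as judged by the Medical Safety Monitor (MSM) and/or DSMB.

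On clotting, Protocol section 1.1 reports that the authors and others "have noted a Tissue Factor mediated pro-coagulant response associated with various types of MSCs". Section 4.1 warns that "the infusion could initiate a VTE event with subsequent cardiopulmonary sequelae of respiratory failure and/or right heart strain/failure". Section 4.4 sets out a coagulation panel, watching for clinical DVT, and 40 mg of Lovenox daily for 7 days from the day before each infusion (not for subjects already on an anticoagulant). Section 4.1 adds re-examination for VTE at follow-up visits. None of these sections sets a number of clots that acts on enrollment or dosing.

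Protocol section 7.3 supplies a discretionary route: "Subsequent review by the MSM, DSMB, IRB or the study sponsor may also result in the suspension of further enrollment". Section 3.6 schedules three infusions per subject, 14 days apart. The SAP says nothing about stopping.

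**The concern.** Clotting is one of the harms that the protocol ties to the cell product itself. Severe respiratory and neurologic events have rules written for them (rules 2 and 3). A clot reaches a rule only if it kills, causes deep sustained hypoxia or ventilation, or is Grade 4-5 and judged temporally related. Below that level the fifth clot counts for no more than the first.

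Two or three lower-grade clots in a small single-arm study could be the early sign of the pro-coagulant effect described in section 1.1. Without a count fixed in advance, whether and when to pause is decided case by case after the events are known. Meanwhile enrolled subjects may still be due one or two infusions, and neither the preamble nor section 7.3 says that these are held.

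**Working it through.** **Rule by rule.** Take a DVT or PE below Grade 4 with no death, no saturation below 80% for more than 3 minutes and no new ventilation. Rule 1: not met. Rule 2: not met. Rule 3: not met, since it covers only cerebral ischemia and seizure. Rule 4: not met, since it needs Grade 4-5. No rule adds events across subjects or infusions, so any number of such clots still fires nothing.

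**Inputs.** n = 24 (Protocol and SAP section 8.1). The documents give no VTE rate, severity split or stopping boundary, so there is no plan figure to reproduce. Two quantities are assumed: p, the VTE risk per subject, and f, the share of VTEs that fire rule 1, 2 or 4. At most one VTE is counted per subject, and subjects are independent.

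The only outside figure is in section 1.1: "A recent meta-analysis evaluated 1012 patients with a variety of clinical conditions, and found only transient fever as an adverse event". It concerns allogeneic MSCs. Read literally as 0 VTEs in 1012, the one-sided 95% upper bound is 1 - 0.05^(1/1012) = 0.00296, about 0.3%. That does not settle the risk of this autologous product, but it makes the low end more plausible.

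**Size of the gap.** The chance of two or more VTE subjects with no rule fired is

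(1 - pf)^24 - (1 - p)^24 - 24p(1 - f)(1 - p)^23.

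At p = 10% and f = 25%: 0.975^24 - 0.90^24 - 24 × 0.075 × 0.90^23 = 0.5446 - 0.0798 - 0.1595 = 0.305.

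| p | f = 10% | f = 25% | f = 50% |
|---|---|---|---|
| 0.3% | 0.19% | 0.13% | 0.06% |
| 2% | 6.6% | 4.5% | 1.9% |
| 10% | 51% | 31% | 11% |

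At f = 25% the value is 1.3% for p = 1%, 17% for p = 5% and 27% for p = 20%. Dividing by P(≥2) gives the chance that no rule fires once two or more subjects have clotted: 56%, 54%, 43% and 28% at p = 0.3%, 2%, 10% and 20%.

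**Choosing a count.** P(≥1) = 1 - (1 - p)^24. P(≥2) subtracts a further 24p(1 - p)^23, and P(≥3) a further 276p²(1 - p)^22. At p = 3%, P(≥2) = 1 - 0.4814 - 0.72 × 0.4963 = 0.161. Here p is the risk over the counting window.

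| p | 1st subject | 2nd subject | 3rd subject |
|---|---|---|---|
| 1% | 21% | 2.4% | 0.2% |
| 2% | 38% | 8.3% | 1.2% |
| 3% | 52% | 16% | 3.4% |
| 5% | 71% | 34% | 12% |
| 10% | 92% | 71% | 44% |
| 20% | 99.5% | 97% | 89% |

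Some clots would come after enrollment has closed, in part because cell processing takes 5 to 7 weeks before dosing. If only the first 18 to 20 subjects count towards a pause in enrollment (assumed), the second-subject trigger fires with probability 55% to 61% at p = 10% and 90% to 93% at p = 20%.

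**The case against.** The strongest reply is that oversight exists and has no grade floor. Section 6 names an MSM, independent monitors and a DSMB, and section 7.3 lets reviewers suspend enrollment and lets the PI stop a subject's participation. VTE is managed through prophylaxis, coagulation tests, a call 24 hours after each infusion and repeat examination. Single-event rules backed by expert review are a coherent scheme for 24 subjects. This stands, and it limits the point: the probabilities above are chances that no automatic rule fires, not that nobody acts.

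A reader might infer that repeated clots would go unreviewed, or that the trial has no VTE trigger anywhere. The documents support neither. Section 7.3 rules out the first. On the second, only the opening of section 6 is in view, and Appendix 3 (the staggered infusion plan for the first four subjects) and any DSMB charter are not, so a trigger may exist there.

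A reader might also infer that rule 4 needs a fixed time window for VTE, because section 4.3 uses "those events occurring within 48 to 72 hours of infusion" for neurologic changes while the Lovenox course runs longer. That does not follow. Rule 4 concerns only Grade 4-5 events, so a window would not close this gap, and leaving the judgement open lets the MSM or DSMB attribute a late severe clot to the cells.

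The rates are assumptions, and nothing in the documents shows a risk of 10% or 20%. This too stands.

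**Conclusion.** The point holds for the supplied text. None of the four listed rules names VTE or counts events. Repeated clots below Grade 4 that avoid rules 1 and 2 fire nothing, and any pause is discretionary. The preamble and section 7.3 are also silent on infusions still due in enrolled subjects.

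The size depends on p and f, both assumed, with no credit given to review under section 7.3. If the true risk is near 0.3%, the gap would seldom matter (0.13% at f = 25%). If it is 5% to 10%, two or more clots with no rule fired has probability 17% to 31% at the same f. This is a gap in pre-specification on a risk that the protocol itself raises. It is worth closing because the remedy is cheap.

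**What to change.** Add to the stopping rules:

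- Any confirmed DVT or PE of any grade, from the start of the first infusion to a stated cutoff after the last infusion (for example 30 days, to be set by the DSMB), is referred promptly to the MSM and DSMB.
- A second subject with such an event pauses enrollment and all further infusions pending DSMB review.

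State in the preamble that any triggered rule also holds pending infusions. Leave rule 4 as it is. If section 6, Appendix 3 or the DSMB charter already contains these provisions, cross-reference them instead.

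The cost is a short amendment that uses the existing monitor, DSMB and VTE assessments, plus an occasional pause for clots unrelated to the cells: 2.4%, 8.3%, 16% and 34% at assumed background risks of 1%, 2%, 3% and 5% per subject over the counting window. The cutoff matters because, without one, a clot reported at the two-year call would count. A first-subject trigger would pause far more often (21% to 38% at 1% to 2%), and a third-subject trigger would detect a 10% risk only 44% of the time, against 71% for the second. The DSMB should revisit the count if it expects a background risk of 3% or more in these patients.
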